9.5. Analyses

9.5.1 *Statistical Methods:*

Descriptive statistics such as age and gender will be reported in means, standard deviations, frequencies, and proportions when appropriate. As recently recommended for pilot studies, ours will focus on point estimates of immune responses and their 80% confidence intervals (CIs) in place of 95% CI used for traditional statistical inferences²⁶. The geometric mean concentration (anti-log of the arithmetic mean of log transformed concentrations) of antibodies while the arithmetic mean of T cell population frequencies and secreted cytokine levels from in vitro antigen-stimulated PBMC will be identified. Comparisons between measurements of immune response in pre- and post-immunization specimens (as specified for primary outcome measurements) will be completed using paired Student's t-test for normally distributed data or Wilcoxon rank signed test for non-normally distributed data. For repeated outcome measurements at 4 time points (as specified in exploratory outcomes), we will use generalized estimating equations (GEE) with unstructured covariance matrix to estimate the time difference. The link function for GEE will be chosen depending on the data type.

9.5.2 *Sample Size and Power:*

There is only one published report describing the anti-gonococcal antibody titers in 10 humans who received 3 immunizations with 4CMenB. The geometric mean titer of serum antibodies directed against whole cell *N. gonorrhoeae* (strain 1291) demonstrated a statistically significant increase between pre (95% CI : 25,906–90,811) and post (95% CI : 49,228–126,115) immunization samples¹⁵. We do not have preliminary data and there is no published data regarding cross-reactive antibodies in 4CMenB-immunized humans against the *N. gonorrhoeae* strain FA1090 (the strain used by our center in both human challenge model and preclinical laboratory studies) or specific FA1090 outer-membrane antigens. Further, there is no published data on anti-gonococcal antibody subtype or levels of these antibodies in mucosal surface secretions in any 4CMenB-immunized humans. Finally, there is no published data regarding cellular immune responses to gonococcal antigens in 4CMenB-immunized individuals. Thus, the proposed study is a pilot study and the power to detect significant immune responses towards *N. gonorrhoeae* antigens is unknown. The study will provide baseline values and variability in measurements for non-immune individuals as well as post immunization measurements for the studied immunologic parameters. We will enroll up to 15 individuals, including similar numbers of men and women; this sample size is proposed based on size of potential participant pool and available funding for the study. The data generated will provide valuable information for how to deploy these assays in human populations receiving 4CMenB immunization for testing efficacy in preventing *N. gonorrhoeae* infection in the future.

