4.3 Study Recruitment and Enrollment Procedures

Potential participants will be recruited from the UNC-Chapel Hill University and surrounding area population. Potential participants will be recruited through flyers posted on the campus and through the UNC email listserv and through Join the Conquest at UNC. Potential participants will contact the study team via telephone or email and a study team member will provide information about the study and review eligibility criteria. Participants will receive a total of \$130 over the course of the study to compensate for time and providing samples related to the study in addition to receiving the benefit of protection from invasive *N. meningitidis* infection as a result of receiving the FDA-approved 4CMenB vaccine over the course of the study. The payments for participation are \$20 provided at screening visit, \$20 at entry visit, and \$30 each at week 5 visit, week 6 visit, and week 7 study completion visit. Participants will be paid at the end of each study visit.

To promote a roughly even balance in the sex at birth of participants, enrollment of additional participants of one sex at birth will be discontinued when enrollment of participants of that sex at birth reaches 8 participants.

Once a candidate has been identified, study details will be carefully discussed with the participant by the study coordinator or study investigator. The participant will be asked to read and sign the IRB approved informed consent form. For participants from whom a signed informed consent form has been obtained, a screening visit will be performed that will include obtaining information related to eligibility, completion of a targeted physical examination, and a point of care urine pregnancy test for female participants of child bearing potential. For participants from

whom informed consent has been obtained, but who are deemed ineligible or who do not enroll into initial immunization step, a Screening Failure Results form must be completed.

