Pharyngeal and vaginal swabs, urine, and serum for measures of *N. gonorrhoeae*-directed antibodies will be collected per the SOE. Antibodies eluted from swabs or present in urine and present in serum from samples collected at entry, week 5, week 6, and week 7 will be tested for *N. gonorrhoeae* antigen-specific antibodies using ELISA. Antibody containing samples will be sent to Regional Biocontainment Laboratory (RBL) Immunology Unit at Duke University for ELISA analysis. The shipped samples will have an identifying sample number (code) derived from the participant's assigned PID and the visit number; no identifying information on the participant's samples will be transmitted to the Duke RBL Immunology Unit and leftover samples will be destroyed or returned to UNC for storage if the participant has agreed to storage of their study specimens. The PI at UNC will keep a master log which links the codes on the stored specimens to the participants. Leftover sera from consenting participants may be used for future *N. gonorrhoeae* research.

6.3.5 *Vaccine/ Injection*

Every effort should be made to administer vaccines within the protocol-defined visit window. Participants who do not receive their first vaccine within 30 days of screening or who do not receive the week 5 vaccine will be prematurely discontinued from the study.

The week 5 visit should be conducted 35 days (\pm 7 days) after the first vaccination (enrollment visit). If the week 5 visit is not within the protocol-specified window, then the vaccine can be given as late as 8 weeks post enrollment.

The week 6 visit should occur 5-9 days after the second dose of vaccine; if week 6 visit samples are not collected, the participant may continue in the study and attend the week 7 visit 12-16 days after receiving the second dose of vaccine. If the week 7 visit is not collected between day 12-16 after the second dose of vaccine, participant will be discontinued from the study.

Vaccination should be deferred at the discretion of the site investigator if the participant is febrile with reported or observed temperature greater than or equal to 38 °C or acutely ill with symptoms (ongoing or present within 7 days of planned vaccination) consistent with infection of the respiratory tract, gastrointestinal tract, urinary tract, or skin/soft tissues.

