9.0 STATISTICAL CONSIDERATIONS**9.1 General Design Issues**

This study is a single center, single arm interventional pilot study in which participants will receive two-doses of the US FDA-approved 4CMenB vaccine according to recommended administration schedule. Blood and mucosal surface specimens will be obtained at 4 study visits. The study population will include 15 individuals aged 18-25 years desiring immunization against group B *N. meningitidis* with no contraindication to vaccination and no known immune compromising medical condition or medication. Enrolled individuals who are discontinued will be replaced.

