- Frequencies of memory, activated, and proliferating CD4+ Tfh cells specific in circulating PBMC obtained at entry visit (prior to first vaccination), week 5 visit (4-6 weeks after first vaccination), week 6 visit (1 week after second vaccination), and week 7 visit (2 weeks after second vaccination) determined by flow cytometry
- The quantity of IFN-g and IL-17 secreted after in vitro stimulation with *N. gonorrhoeae* strain FA1090 Outer-membrane vesicles from circulating PBMC obtained at entry visit (prior to first vaccination), week 5 visit (4-6 weeks after first vaccination), week 6 visit (1 week after second vaccination), and week 7 visit (2 weeks after second vaccination) determined by Bio-Plex Multiplex immunoassay
- The sequence of B-cell receptors found to associate with FA1090 Outer-membrane vesicles through flow cytometry-based cell sorting will be determined using sequencing of PCR amplicons generated using primers for non-variable regions of the B cell receptor

9.3

Sample Size and Accrual

Due to the majority of the target population likely to be undergraduate students, we anticipate that enrollment will be limited to ~1 participant each month in July and August (months when student population residing in Chapel Hill is low) and that the remaining participants will be enrolled at ~6/month in September and October. All Serum and PBMC will be stored until a complete specimen set is obtained from at least 8 subjects; the serum and PBMC specimens will then be transferred to [name] laboratory at Duke University in batch for immunologic assays. We plan to enroll up to 15 subjects so we can obtain a complete specimen set at all 4 study visits for at least 8 subjects.

9.4

Monitoring

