10.3 Criteria for Discontinuation

Removal of participants from study can occur for the following reasons:

10.3.1 *Premature Treatment Discontinuation*

- Treatment-related AEs as discussed in section 7.2.
- Pregnancy or breastfeeding.
- Clinical reasons believed life-threatening by the site principal investigator, even if not addressed in section 7.2.

10.3.2 *Premature Study Discontinuation*

- Request by the participant to discontinue treatment prior to receiving second immunization or to withdraw from study.
- Request of the primary care provider if s/he thinks the study is no longer in the best interest of the participant.
- Failure to start study vaccination within 30 days after screening or to receive second vaccination within 8 weeks of initial dose.
- Failure to attend week 6 or week 7 study visits within the indicated time window.

- At the discretion of the IRB, NC TraCS, industry supporter, FDA, Office for Human Research Protections (OHRP), investigator, or other country-specific government agencies as part of their duties to ensure that research participants are protected.

10.4 **Deviations from the Protocol**

The investigator may implement a deviation from, or a change of, the protocol to eliminate an immediate hazard(s) to study participants without prior IRB approval. As soon as possible, the implemented deviation or change, the reasons for it, and, if appropriate, the proposed protocol amendment(s) should be submitted to:

- a) IRB for review and approval
- b) to the sponsor for agreement and, if required
- c) to the appropriate regulatory authority(ies)

10.5 **Clinical Site Monitoring and Record Availability**

Personnel from the Global HIV Prevention and Treatment Clinical Trials Unit at the University of North Carolina (UNC) will monitor the trial for quality assurance. These monitors will review all source documents used in the preparation of the case report forms to assure proper conduct of the trial and proper collection of the data.

10.6 **Required Documentation**

Before the study can be initiated, the following documentation must be provided to the IGHID Regulatory Office at the University of North Carolina.

- A copy of the official IRB approval letter for the protocol and informed consent(s)
- IRB membership list
- CVs and medical licensure for the principal investigator and any associate investigators who will be involved in the study
- A copy of the IRB-approved consent form(s)

10.7 **Adherence to the Protocol**

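### The GEE for the four-visit exploratory endpoints names no small-sample variance correction or t reference; with 15, 8 or 7 participants, an uncorrected run would give nominal 80% intervals that cover about 76%, 73% or 72%

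*Combined protocol and SAP*

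**What the plan says.** Section 9.5.1 says that reporting will centre on "point estimates of immune responses and their 80% confidence intervals (CIs". Pre/post comparisons for the primary outcomes use a paired t-test or a "Wilcoxon rank signed test for non-normally distributed data". For exploratory outcomes at four time points the only method given is GEE: "we will use generalized estimating equations (GEE) with unstructured covariance matrix to estimate the time difference". The link is left to depend on the type of data. No section names a variance estimator, a small-sample correction, a reference distribution or a fallback for the GEE.

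Section 9.2.2 lists ten continuous four-visit endpoints: seven antibody endpoints, plus CD8 frequencies, Tfh frequencies and secreted cytokines. Four of the antibody endpoints are single-sex (two vaginal, two urine). An eleventh four-visit endpoint, the immunoblot, is qualitative.

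On numbers, sections 9.3 and 9.5.2 allow up to 15 participants. Section 9.3 seeks "a complete specimen set at all 4 study visits for at least 8 subjects". Section 4.3 says that "enrollment of additional participants of one sex at birth will be discontinued when enrollment of participants of that sex at birth reaches 8 participants". Section 9.1 adds: "Enrolled individuals who are discontinued will be replaced".

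On a missed week 6, section 6.3.5 says that "if week 6 visit samples are not collected, the participant may continue in the study and attend the week 7 visit". Section 10.3.2 lists among the reasons for removal: "Failure to attend week 6 or week 7 study visits within the indicated time window".

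**The concern.** The sandwich variance in GEE is justified for a large number of independent clusters. Here the clusters are participants, and there are 15 at most. Without a correction the sandwich variance is biased downwards, and a normal quantile ignores the fact that the variance is estimated from few people. Both effects narrow the interval.

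The study presents itself as estimating responses with intervals rather than testing hypotheses, and it is meant to supply baseline values and variability for later work. Error bars that are too narrow would overstate what was learned. The effect is largest for the genital-tract antibody endpoints. They have the fewest participants, and section 9.5.2 says nothing has been published on mucosal antibody levels after this vaccine.

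**Working it through.** The plan gives no power, coverage or interval-width figure to reproduce. Section 9.5.2 says power is unknown and that the sample size rests on the participant pool and funding. The check is therefore of interval coverage.

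**Inputs.** Confidence level 80% (section 9.5.1), so z = 1.2816. N = 15 is the enrolment ceiling (sections 9.3 and 9.5.2). N = 8 is the cap per sex (section 4.3). N = 7 is 15 - 8, which is derived and not stated.

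**Assumptions, none stated in the documents.** One mean per visit, complete data, identity link, normally distributed within-person differences (for antibodies, on the log scale), an uncorrected sandwich standard error and a normal quantile.

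**Step 1.** With one mean per visit and complete data, the GEE estimate of a visit-minus-entry change is the mean paired difference, whatever the working matrix. The unstructured matrix therefore does not alter the interval width in this case.

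**Step 2.** With s² the usual sample variance of the differences, the uncorrected sandwich variance is ((N-1)/N) × s²/N. The paired-t variance is s²/N. The standard error is thus too small by a factor sqrt((N-1)/N).

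**Step 3.** Coverage with z is P(|t on N-1 df| < 1.2816 × sqrt((N-1)/N)). Width relative to the exact interval is 1.2816 × sqrt((N-1)/N) / t(0.90, N-1). If the standard error is right and only z replaces t, coverage is P(|t on N-1 df| < 1.2816).

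| N | t(0.90, N-1) | 1.2816 × sqrt((N-1)/N) | Coverage, uncorrected SE and z | Relative width | Coverage, correct SE and z |
|---|---|---|---|---|---|
| 15 | 1.345 | 1.238 | 76.4% | 0.920 | 77.9% |
| 8 | 1.415 | 1.199 | 73.0% | 0.847 | 75.9% |
| 7 | 1.440 | 1.187 | 72.0% | 0.824 | 75.3% |

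The uncorrected intervals are about 8%, 15% and 18% too narrow.

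**Step 4: simulation.** 1,000 GEE fits per N in standard software (unstructured matrix, robust SE, z) covered 75.9%, 73.5% and 71.2%, with simulation error of about 1.4 points. This agrees with the table. A model-based SE with z in the same runs covered 77.3%, 75.9% and 72.8%.

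**Step 5: the correction.** In this setting each participant's leverage is 1/N, so Kauermann-Carroll multiplies the variance by N/(N-1). With t on N-1 df the result is the paired-t interval, which covers exactly 80% for normal differences. Widening relative to the uncorrected interval is 1/0.920 = 1.09, 1/0.847 = 1.18 and 1/0.824 = 1.21.

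**Step 6: skewed untransformed endpoints (CD8, Tfh, cytokines).** The documents give no variability for these, so the result depends on what is assumed. For lognormal data with correlation 0.6, corrected coverage was:
- log-SD 0.8 to 1.2 and a 1.5- to 3-fold rise: 69-78% at N=15 and 66-77% at N=8 (uncorrected 66-74% and 61-70%);
- log-SD 0.3 to 0.5 and a 1- to 3-fold change: 78-80% at N=15 and 77-80% at N=8;
- no change, any log-SD from 0.3 to 1.2: about 80-81%.

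**Step 7: stability of the fit.** With 15% of week 6 values missing at random (assumed), the unstructured fit failed numerically in 11 of 600 data sets at N=8 and 48 of 600 at N=7.

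**The case against.** The strongest reply is that the plan is silent rather than wrong. GEE is a legitimate method, and nothing in the protocol prescribes an uncorrected sandwich or a normal quantile. An analyst who chose a t-based correction would have no shortfall under the assumptions above. This stands: the coverage figures are conditional, and the documents do not support reading them as a prediction that the published intervals will be too narrow. What remains is that z still falls short with a correct or model-based SE, so the ordinary ways of running this GEE give intervals that are too narrow unless the correction is named.

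It is also fair to say that section 9.5.1 does not expressly attach the 80% interval to the GEE contrasts. That is the natural reading of a stated general focus, but it is an inference.

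A reader might infer from section 9.3 that endpoints using all participants will rest on 8 people or, if 8 complete sets split evenly by sex, single-sex endpoints on 4. The documents do not plan for this. Eight complete sets is a minimum and a trigger for batching, section 9.1 replaces discontinued participants, and GEE can use participants with incomplete data. For endpoints using everyone, the planned case is N=15. The floor matters only for a fallback: with 4 participants, residuals about four visit means have rank at most 3, so a 4×4 unstructured matrix is singular.

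It can further be said that, with complete data, the paired methods would give the same interval more simply. That is true. GEE earns its place only when some visits are missing. Whether that can happen is unclear, because removal under section 10.3.2 is worded as something that can occur, and it concerns attendance where section 6.3.5 concerns samples. The two sections leave an ambiguity more than a flat contradiction.

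**Conclusion.** The concern holds as a minor, conditional gap. With an uncorrected sandwich SE and z, complete data, an identity link and normal differences, nominal 80% intervals cover 76.4% (N=15), 73.0% (N=8) and 72.0% (N=7). With only z in place of t they cover 77.9%, 75.9% and 75.3%. The omission and the arithmetic are certain; which estimator will be used is not known.

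Three stronger readings are not supported. The primary analyses are unaffected, because they use paired tests. The unstructured matrix is not the cause of the shortfall with complete data. Nor does the correction guarantee 80% for every endpoint: for skewed untransformed measures it reduces the shortfall by an amount that depends on variability the documents do not give. No decision rule depends on any of these intervals.

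**What to change.** Keep the GEE, the unstructured matrix and the sentence on the link, and add to section 9.5.1:

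> For continuous endpoints, 80% CIs for each post-entry visit versus entry will use a small-sample corrected sandwich variance (Kauermann-Carroll) with a t reference on N-1 df, N being the participants analysed for that endpoint; if the unstructured fit does not converge or its estimated matrix is not positive definite, the paired-difference t interval will be used.

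The estimator should be named and not left at small-sample corrected. A stronger correction (Mancl-DeRouen) with t covered 81.0%, 82.7% and 82.0% in the complete-data fits, slightly above nominal. The sentence does not cover the qualitative immunoblot endpoint.

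The cost is intervals about 9% (N=15), 18% (N=8) and 21% (N=7) wider than the uncorrected ones, and a protocol amendment submitted to the IRB under section 10.8. No extra participants, samples or assays are needed.

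Separately, sections 6.3.5 and 10.3.2 should be reconciled on whether a participant with a missed week 6 visit stays in the study, since this decides whether the GEE has missing visits to handle.

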10.0 STUDY MANAGEMENT

10.1 Institutional Review Board (IRB) Review and Informed Consent

This protocol and the informed consent document and any subsequent modifications (amendments) will be reviewed and approved by the IRB or ethics committee responsible for oversight of the study.

It is expected that the IRB will have the proper representation and function in accordance with federally mandated regulations. The IRB should approve the consent form(s) and protocol.

In obtaining and documenting informed consent, the principal investigator should comply with the applicable regulatory requirement(s), and should adhere to Good Clinical Practice (GCP) and to ethical principles that have their origin in the Declaration of Helsinki.

Before recruitment and enrollment onto this study, the participant will be given a full explanation of the study and will be given the opportunity to review the consent form(s). Each consent form must include all the relevant elements currently required by the FDA Regulations and local or state regulations, which include elements such as the purpose of the study, the procedures to be followed, and the risks and benefits of participation. Once this essential information has been provided to the participant and the investigator is assured that the participant understands the implications of participating in the study, the participant will be asked to give consent to participate in the study by signing an IRB-approved consent form.

Prior to a participant's participation in the trial, the written informed consent form(s) should be signed and personally dated by the participant or the participant's legally authorized representative (legal guardian or person with power of attorney for participants who cannot consent for themselves), and by the person who conducted the informed consent discussion.

A copy of the consent form will be given to the participant or legal guardian, and this fact will be documented in the participant's record.

